### 2.3 DRUG PROFILE

Saroglitazar, a dual PPAR agonist with predominantly PPAR $\alpha$  and a moderate PPAR $\gamma$  agonist activity, [REDACTED]

**Preclinical Experience**

[REDACTED]

[REDACTED]

[REDACTED]

[REDACTED]

[REDACTED]

[REDACTED]

**Clinical Experience**

Saroglitazar Maximum Tolerated Dose in Phase 1 was 16 mg/day for 10 days and was found to be well tolerated. From preclinical studies and Phase I trial, it appeared that Saroglitazar had a promising safety and efficacy profile.

In Phase 1 study of healthy human volunteers, Saroglitazar was found to be well tolerated in single and multiple dose studies without any serious side effects [11].

A Phase 2 study was conducted to evaluate the efficacy and safety of Saroglitazar on the lipid and glucose profile in dyslipidemic patients with normal glucose tolerance, impaired glucose tolerance or diabetes.

[REDACTED]

[REDACTED]

[REDACTED]

A Phase 3 study was conducted to evaluate the efficacy and safety of Saroglitazar in diabetic dyslipidemic patients as compared to pioglitazone, there was significant reduction in the TG levels at all visits as compared to baseline. Similarly there were significant reductions in the very low density lipoprotein (VLDL) and total cholesterol levels as compared to pioglitazone. In another Phase 3 study of Saroglitazar in diabetic dyslipidemic patients not controlled with atorvastatin 10 mg revealed significant reduction in the TG levels as compared to placebo. Significant reduction in the low density lipoprotein (LDL) cholesterol, total cholesterol and apolipoprotein B levels with Saroglitazar 4 mg was observed as compared to baseline.

 Zydus Discovery DMCC	CLINICAL TRIAL PROTOCOL Saroglitazar Magnesium – Phase 2 SARO.17.004	CONFIDENTIAL Page 25 of 76
---	---	---

### 3 STUDY OBJECTIVES

To evaluate the safety and efficacy of Saroglitazar Magnesium 2 mg and 4 mg in patients diagnosed with non-alcoholic steatohepatitis (NASH).

#### 3.1 PRIMARY OBJECTIVE

To evaluate the changes in NAFLD Activity Score (NAS) at week 24 from baseline and with no worsening of fibrosis in NASH patients.

#### 3.2 SECONDARY OBJECTIVES

1. To evaluate the percentage of responders in the treatment groups.
2. To evaluate the percentage of responders, defined as the disappearance of steatohepatitis over the time period up to Week 24 in patients treated with Saroglitazar Magnesium 2 mg and 4 mg.
3. Changes from baseline to Week 24 in Saroglitazar Magnesium 2 mg and 4 mg for the following parameters:
  - Stage of steatosis, lobular inflammation and ballooning
  - Stages of fibrosis
  - Liver function tests (alanine aminotransferase, aspartate aminotransferase, alkaline phosphatase, gamma-glutamyl transferase, direct bilirubin, total proteins and albumin).
  - Lipid profile parameters (triglyceride, small dense low density lipoprotein, high density lipoprotein, low density lipoprotein, very low density lipoprotein, total cholesterol and non HDL cholesterol Apo lipoprotein A1 and Apo lipoprotein B).
  - Insulin resistance and glycemic control parameters (fasting plasma glucose, glycosylated hemoglobin, fasting insulin, C-peptide, adiponectin, homeostasis model assessment beta and homeostasis model assessment for insulin resistance).

	Approved by: [name] [name]	Protocol No.: SARO.17.004.02.PROTOCOL Version No.: 2.0
---	------------------------------------	---

 Zydus Discovery DMCC	CLINICAL TRIAL PROTOCOL Saroglitazar Magnesium – Phase 2 SARO.17.004	CONFIDENTIAL Page 26 of 76
---	---	---

4. To assess the safety of Saroglitazar Magnesium 2 mg and 4 mg in patients with non-alcoholic steatohepatitis over 24 weeks of treatment.

	Approved by: [name] [name]	Protocol No.: SARO.17.004.02.PROTOCOL Version No.: 2.0
---	------------------------------------	---

 Zydus Discovery DMCC	CLINICAL TRIAL PROTOCOL Saroglitazar Magnesium – Phase 2 SARO.17.004	CONFIDENTIAL Page 27 of 76
--	---	---

#### 4 STUDY POPULATION

Subjects clinically suspected of NASH and having laboratory evidence of abnormally elevated liver function tests (LFT) suggestive of NASH and confirmed histologically by biopsy will be recruited for the study. The histological evidence of NASH is defined as NAS  $\geq 4$  with a minimum score of 1 for all of its three components [steatosis, hepatocyte ballooning and lobular inflammation].

If the subject has consumed restricted medications but is otherwise considered eligible to be enrolled in this study by the Investigator, then a minimum of 1 month wash out period will be instituted before the screening visit.

##### 4.1 NUMBER OF SUBJECTS PLANNED

A total 15 patients will be enrolled from a multiple centers in a ratio of 2:2:1 to have 6 patients in Saroglitazar Magnesium 2 mg, 6 patients in Saroglitazar 4 mg and 3 patients in placebo arm for 24 weeks.

##### 4.2 INCLUSION CRITERIA

1. Patients able to provide written informed consent for participation in this trial.
2. Males or females, 18 to 75 years of age, both inclusive.
3. Female must be either of non-child bearing potential (surgically sterilized at least 6 months prior to screening or postmenopausal) or using one or more methods of contraception.
4. Histologic confirmation of NASH without cirrhosis (fibrosis stage 0, 1, 2, or 3) from liver biopsy performed either during the screening period or no more than 6 months prior to the first visit, with a NAS of  $\geq 4$  and a score of at least 1 in each (steatosis scored 0-3, ballooning scored 0-2 and lobular inflammation scored 0-3). If biopsy was performed within 6 months of screening, the slides, biopsy material or block should be available for baseline documentation. Such patients, whose historical biopsy report is available, should not use medications suspected of having an effect on NASH for at least 3 months prior to the screening.
5. BMI  $\geq 25$  kg/m^2.

	Approved by: [name] [name]	Protocol No.: SARO.17.004.02.PROTOCOL Version No.: 2.0
---	---	---

 Zydus Discovery DMCC	CLINICAL TRIAL PROTOCOL Saroglitazar Magnesium – Phase 2 SARO.17.004	CONFIDENTIAL Page 28 of 76
--	---	---

6. For hypertensive patients, blood pressure must be controlled by a stable dose of antihypertensive medications for at least 3 months prior to screening (and the stable dose can be maintained throughout the study)
7. Patients with type 2 diabetes mellitus may be included if they fulfil the following criteria;
  - a. Stable therapeutic regimen as defined by no changes in oral agents or dose for at least 3 months before screening and the stable dose can be maintained throughout the study.
  - b. HbA1c  $\leq$  9.5%.
8. Patients agree to comply with the study procedure.

#### 4.3 EXCLUSION CRITERIA

1. Pregnant and lactating female.
2. Positive pregnancy test.
3. Patients with history of myopathies or evidence of active muscle diseases.
4. Patients with history of alcohol consumption of  $>30$  gm/day for men,  $>20$  gm/day for women for consecutive previous 2 years and/or drug abuse.
5. Known allergy, sensitivity or intolerance to the study drug or formulation ingredients.
6. Participation in an interventional clinical study and/or receipt of any investigational medication within 3 months prior to screening.
7. History of malignancy in the past 5 years and/or active neoplasm with the exception of superficial, non-melanoma, skin cancer.
8. Any of the following laboratory values at screening:
  - a. Direct bilirubin  $>1.5$  mg/dL
  - b. Serum albumin  $<2.5$  g/dL
  - c. Estimated glomerular filtration rate (eGFR)  $<60$  mL/min/1.73m^2
  - d. Serum alanine aminotransferase (ALT) or aspartate aminotransferase (AST)  $>200$  IU/L
  - e. Patients with international normalized ratio (INR)  $>1.5$
  - f. Creatinine kinase  $\geq 1.5$  ULN

	Approved by: [name] [name]	Protocol No.: SARO.17.004.02.PROTOCOL Version No.: 2.0
--	------------------------------------	---

 Zydus Discovery DMCC	CLINICAL TRIAL PROTOCOL Saroglitazar Magnesium – Phase 2 SARO.17.004	CONFIDENTIAL Page 29 of 76
--	---	---

- g. Lipase  $\geq$ ULN
  - h. Amylase  $\geq$  ULN.
9. Unstable cardiovascular disease, including:
- a. unstable angina, (i.e., new or worsening symptoms of coronary heart disease within the 3 months preceding screening), acute coronary syndrome within the 6 months preceding Screening, acute myocardial infarction within the 3 months preceding screening or heart failure of New York Heart Association class (III – IV) or worsening congestive heart failure, or coronary artery intervention, within the 6 months preceding screening
  - b. history of (within 3 months preceding Screening) or current unstable cardiac dysrhythmias
  - c. uncontrolled hypertension (systolic blood pressure [BP] > 155 mmHg and/or diastolic BP > 95 mmHg)
  - d. Stroke or transient ischemic attack within the 6 months preceding screening.
10. Previous history of bladder disease and/or hematuria.
11. Previous liver biopsy that demonstrated presence of cirrhosis or radiologic imaging consistent with cirrhosis or portal hypertension.
12. Type 1 diabetes mellitus.
13. Use of drugs that are known CYP2C8 inhibitors/substrate.
14. Use of drugs associated with a clinical or histological picture consistent with fatty liver disease or NASH for more than 12 consecutive weeks in the 1 year prior to start of the study; (these include amiodarone, tamoxifen, methotrexate, glucocorticoids, anabolic steroids, tetracyclines, estrogens, valproate/valproic acid, chloroquine, anti-HIV drugs).
15. History of thyroid disease (hypothyroid patients who are euthyroid on thyroid hormone replacement can be included).
16. History of, or current, cardiac dysrhythmias.
17. History of bariatric surgery, or undergoing evaluation for bariatric surgery.
18. Patients with a >10% weight loss in the 3 months prior to screening.
19. History or other evidence of severe illness or any other conditions that would make the patient, in the opinion of the Investigator, unsuitable for the study (such as poorly

	Approved by: [name] [name]	Protocol No.: SARO.17.004.02.PROTOCOL Version No.: 2.0
---	------------------------------------	---

 Zydus Discovery DMCC	CLINICAL TRIAL PROTOCOL Saroglitazar Magnesium – Phase 2 SARO.17.004	CONFIDENTIAL Page 30 of 76
--	---	---

controlled psychiatric disease, coronary artery disease, HIV or active gastrointestinal conditions that might interfere with drug absorption).

20. Patients on any treatment with other drugs used for treatment of NASH [pentoxifyllin, ursodeoxycholic acid, antioxidants such as vitamin E (>800 IU/day), glutathione, orlistat, betaine, incretin mimetics or non-prescribed complementary alternative medications (including dietary supplements, megadose vitamins, herbal preparations and special teas)] or any medicine in clinical trials for NASH. *(However, patients who are taking stable dose of vitamin E for at least 3 months prior to screening will be enrolled in the study).*
21. History of other causes of chronic liver disease [autoimmune, primary biliary cirrhosis, hepatitis B virus (HBV) and hepatitis C virus (HCV), Wilson disease, alpha-1-antitrypsin deficiency, hemochromatosis etc.

#### 4.4 SUBJECT WITHDRAWAL

Subjects may withdraw from the study at any time for any reason without prejudice to his or her future medical care. Although a subject is not obliged to give his/her reason for withdrawing prematurely, the PI will make a reasonable effort to obtain the reason while fully respecting the subject's rights. If there is a medical reason for withdrawal, the subject will remain under the supervision of the PI for follow-up of AE(s) as detailed in *Section 9.4.3*. Every effort will be made to continue clinical and/or laboratory follow-up, as appropriate, in subjects who wish to withdraw from the study drug ) and reasonable efforts will be made to contact a subject who fails to attend any follow-up appointments, in order to ensure that he/she is in satisfactory health. A subject's withdrawal of consent and agreement to undergo a final examination will be documented on the case report form (CRF) and on the PI's copy of the ICF, which will be countersigned and dated by the subject.

As far as possible, all assessments scheduled for End-of-treatment must be performed on all subjects who receive the study drug but do not complete the study according to protocol. However, liver biopsy should be performed in those subjects who have completed at least 12 weeks of the study treatment.

	Approved by: [name] [name]	Protocol No.: SARO.17.004.02.PROTOCOL Version No.: 2.0
---	---	---

#### 4.4.1 Screen Failure

If a subject is termed as a screen failure for not meeting the inclusion/exclusion criteria, the subject may be rescreened only after obtaining Sponsor approval. The Sponsor may approve for rescreening those cases in which subjects failed the screening parameters within a narrow margin. Screening laboratory tests may be repeated following the approval of the Sponsor or its designee if the laboratory test results seem implausible or inaccurate.

At least 35 days from the date of the subject’s initial screening will need to elapse prior to rescreening a subject. The subject will need to be rescreened under a new screening number and a new informed consent must be obtained. A screen failure occurs when a patient who has signed the informed consent form (ICF) does not meet all the entry criteria outlined in this protocol and has not been enrolled or received study drug. No study procedures (including End-of-treatment procedures) will be performed for these patients. For patients who fail to meet the inclusion criteria or who meet 1 or more of the exclusion criteria, the PI (or designee) will document on a screening log the reason for the screening failure.

#### 4.5 DISCONTINUATION OF SUBJECTS FROM THE STUDY OR STUDY DRUG

A subject may be discontinued from the study for any of the following reasons:

1. Occurrence of a serious or intolerable AE and if considered in Investigator’s/Medical Expert’s opinion that it is not in the subject’s best interest to continue.
2. The Sponsor, IRB/IEC or PI or the regulatory terminates the study.
3. Either the PI or the Sponsor decides that discontinuing the study or discontinuing the subject is in the subject’s best interest.
4. The subject is lost to follow-up.
5. Any subject who wishes to withdraw his/her consent for participation in the study.
6. In case a subject becomes pregnant, then she will be withdrawn from the study.

A subject may also be discontinued from study drug/study by the Regulatory Authorities or IRB/IEC.

A study completion CRF, which includes the reason for discontinuation, must be completed for all subjects who are discontinued from the study. If the subject is discontinued prematurely, the study completion CRF should clearly indicate the reason for discontinuation. If the subject

 Zydus Discovery DMCC	CLINICAL TRIAL PROTOCOL Saroglitazar Magnesium – Phase 2 SARO.17.004	CONFIDENTIAL Page 32 of 76
--	---	---

discontinues due to an AE, an AE CRF must be completed. The AE must be followed by medical attention to satisfactory resolution and all study data related to the subject will be reported.

Every effort will be made to continue clinical and laboratory follow-up, as appropriate, in subjects who are withdrawn or in whom the study drug is stopped by the PI.

#### 4.6 STOPPING CRITERIA FOR INDIVIDUAL PATIENTS

The following clinical events warrant discontinuation of study drug; however, the patient will continue to be followed for safety, liver function tests and lipid levels until the event has resolved, i.e., clinical laboratory value(s) has/have returned to baseline or is/are no longer of clinical significance. Discontinuation of study drug will only occur if mandated by safety events as defined below:

- Discontinue any patient with an adverse event of Common Terminology Criteria for Adverse Event (CTCAE) of grade 3 or higher that is possible or likely drug-related and discontinue any patient with an adverse event of CTCAE of grade 4 regardless of attribution to drug.
- Serious AE (SAE) that may be related to the drug and warrant discontinuation as per discretion of the PI;
- In the opinion of the PI, continuation of study drug poses a health risk to the patient.
- Evidence of drug induced liver injury requiring study drug discontinuation as shown in the algorithm below.
  - If patients with abnormal baseline liver indices develop elevations of AST or ALT greater than 2 times baseline or total bilirubin greater than 1.5 X baseline values while on study, testing should be repeated within 48-72 hours. If there are persistent elevations in ALT or AST greater than 2 X baseline or total bilirubin greater than 1.5 X baseline values, then close observation (see DILI Guidance for definition, testing and physical examination 2-3 times per week) should be initiated or drug should be discontinued.
  - A decision to discontinue or temporarily interrupt a study drug should be considered based on factors that include how much higher baseline ALT and AST were relative to the upper limit of normal (ULN) and how much the on study ALT

	Approved by: [name] [name]	Protocol No.: SARO.17.004.02.PROTOCOL Version No.: 2.0
--	------------------------------------	---

 Zydus Discovery DMCC	CLINICAL TRIAL PROTOCOL Saroglitazar Magnesium – Phase 2 SARO.17.004	CONFIDENTIAL Page 33 of 76
--	---	---

and AST levels have increased relative to baseline, in addition to whether there is concomitant elevation of bilirubin or INR.

- The criteria for discontinuing or temporarily interrupting study drug are as follows:
  - When the baseline values were  $\geq 1.5 \times \text{ULN}$  but  $< 5 \times \text{ULN}$ , discontinue if ALT or AST increases to  $> 3 \times$  baseline value
  - Discontinue if ALT or AST increase  $> 2 \times$  baseline value AND the increase is accompanied by a concomitant total bilirubin level increase to  $> 2 \times$  baseline value OR the INR concomitantly increases by  $> 0.2$
  - Discontinue and evaluate any patient with elevations of ALT/AST if sign or symptoms of right upper quadrant pain (RUQ), abdominal pain, anorexia, nausea, vomiting fever, eosinophilia and/or rash are present
  - If a patient lives in a remote area, they can be tested locally and the results be communicated to the Investigator site promptly.

[figure not shown]

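### The liver algorithm in Protocol 4.6 gives patients with normal baseline indices no timed ALT/AST retest, and has no ALT/AST-only stop for baselines below 1.5 x ULN

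*Protocol*

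**What the plan says.** Protocol 4.6, repeated in the synopsis under the same title, lists the events that end study drug. Its liver algorithm has these parts:

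- **Retest.** "If patients with abnormal baseline liver indices develop elevations of AST or ALT greater than 2 times baseline", the tests are repeated within 48-72 hours. A total bilirubin trigger (above 1.5 x baseline) sits in the same sentence under the same restriction.
- **If the rise persists:** "then close observation (see DILI Guidance for definition, testing and physical examination 2-3 times per week) should be initiated or drug should be discontinued".
- **Judgment.** One bullet begins "A decision to discontinue or temporarily interrupt a study drug should be considered based on factors that include how much higher baseline" and goes on to weigh the enzymes against ULN and the size of the on-study rise. This applies at any baseline but names no value, time or action.
- **Stop on ALT/AST alone.** For baselines of at least 1.5 and below 5 x ULN, "discontinue if ALT or AST increases to" more than 3 x baseline. This is the only such number.
- **Combined stops, any baseline.** ALT/AST above 2 x baseline together with a bilirubin or INR rise; or, for symptoms, "Discontinue and evaluate any patient with elevations of ALT/AST if sign or symptoms of right upper quadrant pain" or other listed complaints are present.

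The same section has general stops: a possibly or likely drug-related event of CTCAE grade 3 or higher; for grade 4, "discontinue any patient with an adverse event of CTCAE of grade 4 regardless of attribution to drug"; and "In the opinion of the PI, continuation of study drug poses a health risk to the patient".

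On who may be enrolled, section 4 describes "Subjects clinically suspected of NASH and having laboratory evidence of abnormally elevated liver function tests (LFT) suggestive of NASH". Section 4.2 has no liver-test criterion. Section 4.3 sets only upper limits for ALT and AST (above 200 IU/L is excluded). Section 7.1 enrols on those criteria plus biopsy.

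**The concern.** A patient with biopsy-proven NASH and wholly normal liver tests can satisfy every numbered entry criterion. If ALT then rises several-fold without symptoms and without a bilirubin or INR change, no part of the liver algorithm fixes a response. The timing of a repeat test is left to the investigator. Two sites could handle the same value differently, and the next scheduled sample may be weeks away.

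A patient with some abnormal index but ALT/AST below 1.5 x ULN is better covered, by the retest and the observe-or-stop step. That patient still has no mandatory stop on ALT/AST alone. Within the algorithm, then, the same on-study value draws the weakest fixed response where the relative rise is largest.

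**Working it through.** **Step 1: which fixed rule applies to an isolated, asymptomatic ALT/AST rise (4.6).**

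- Baseline at least 1.5 and below 5 x ULN: retest above 2 x baseline, mandatory stop above 3 x baseline.
- Baseline below 1.5 x ULN with some abnormal index: retest above 2 x baseline, then observe or stop if it persists; no mandatory stop.
- All indices normal: no fixed retest and no ALT/AST-only stop in the algorithm.

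**Step 2: what other sections add for the all-normal patient.** Section 6.4 leaves repeat testing to medical indication. Section 9.4.1 requires clinically significant laboratory values to be followed with repeat tests until they normalise, stabilise or lose significance, but the investigator decides significance. Section 9.4.3 requires adverse events to be monitored until laboratory values return to baseline or stabilise acceptably. None of these states an interval.

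**Step 3: the interval left by the schedule.** SAP 7.3.4 (Laboratory Results) places on-treatment samples at Weeks 6, 12, 18 and 24, which is 6 x 7 = 42 days apart. With the protocol's windows of 7 days either side, Visits 3 and 4 can fall on Days 43 - 7 = 36 and 85 + 7 = 92, a gap of 56 days.

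**Step 4: size of the discontinuity.** ULN is an assumption, because the reference ranges in Protocol Appendix 3 are not shown; 30, 35, 40 and 55 IU/L are used. At its lower boundary the existing stop acts above 3 x 1.5 x ULN = 4.5 x ULN, which is 135, 157.5, 180 and 247.5 IU/L. For each ULN, take the lowest whole-number baseline in the stop band and the first whole value that forces a stop from it (3 x baseline + 1). Then apply that value to a baseline 1 IU/L lower, and to a normal baseline of ULN - 2 with all indices normal.

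| Assumed ULN | On-study value | Must stop from | Retest only, 1 IU/L lower | Neither in the algorithm, normal baseline |
|---|---|---|---|---|
| 30 | 136 | 45 (136/45 = 3.02 x) | 44 (trigger above 88; 3.09 x) | 28 (136/28 = 4.86 x) |
| 35 | 160 | 53 (160/53 = 3.02 x) | 52 (trigger above 104; 3.08 x) | 33 (160/33 = 4.85 x) |
| 40 | 181 | 60 (181/60 = 3.02 x) | 59 (trigger above 118; 3.07 x) | 38 (181/38 = 4.76 x) |
| 55 | 250 | 83 (250/83 = 3.01 x) | 82 (trigger above 164; 3.05 x) | 53 (250/53 = 4.72 x) |

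In the fourth column, a rise that persists on retest leads to close observation or discontinuation. The ordering is the same at every ULN tried.

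**Step 5: what cannot be computed.** Sections 9.4.1 and 9.4.4.1 name CTCAE 4.03 or higher for grading, but no ALT/AST grade limits are printed. Whether any value in the table would already be a grade 3 or 4 event cannot be determined from the documents. Nor do they show how many of the 15 patients would have normal baseline indices.

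**The case against.** A reader might infer that a patient with a normal baseline has no stopping rule, or would stay on drug at 181 IU/L. The documents do not support that. The CTCAE stops apply at every baseline and may already act at such a value. The causality scale in 9.4.4.2 counts an event of unknown association, not reasonably explained by other conditions, as possibly related; an unexplained ALT rise recorded as an adverse event could fit. The investigator-opinion stop is itself on the 4.6 list. Section 6.4 requires a written reason for not reporting an abnormal result that needs further diagnostic testing. Section 4.5 allows discontinuation in the subject's best interest, 7.1 calls for investigator review of all laboratory reports, and 7.4 provides DMC review. All of this stands, and it confines the point to the fixed liver rules and the retest timing.

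Second, if section 4 is enforced as an entry requirement, the all-normal group is empty. That is also fair. The remaining patients below 1.5 x ULN would then have the retest and the observe-or-stop step, and leaving the final stop to judgment would be a defensible choice. But raised liver tests are not among the numbered criteria that 7.1 applies at enrolment.

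Third, the DILI Guidance that 4.6 cites is not available and could hold further thresholds. However, 4.6 cites it when describing close observation, and the written algorithm reads as complete without it.

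Fourth, thresholds tied to ULN do not equalise relative rises. At ULN 40, an all-normal patient with ALT 20 would be retested only above 80 (4 x baseline), while the same ALT with an abnormal GGT is retested above 40; a stop above 180 is 9 x that baseline. This is correct. The proposal closes the missing rule and the step at 1.5 x ULN, and claims no more.

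**Conclusion.** The point holds as a cheap improvement to a safety rule. The text establishes three things: the timed retest and its follow-on step are limited to abnormal baseline indices; the only ALT/AST-only stop is limited to baselines from 1.5 to below 5 x ULN; and normal liver tests do not bar entry. The practical consequence is that, for an all-normal patient with an isolated, asymptomatic rise, the repeat has no fixed time and scheduled samples are 42 days apart nominally (56 at the edge of the windows).

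The multiples of 4.72 to 4.86 x baseline with neither rule triggered illustrate the liver algorithm alone and rest on assumed ULNs of 30 to 55 IU/L. They do not show that such a patient would continue treatment, because the CTCAE stops may already apply. The case for extending the retest is firm. The case for a fixed stop number is softer and depends on hepatology advice.

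**What to change.** **Main change.** Amend 4.6 and the synopsis so that the 48-72 hour retest and, if the rise persists, close observation or discontinuation apply to all patients. The ALT/AST trigger would be above 2 x ULN when all baseline indices are normal (60, 70, 80 or 110 IU/L at ULN 30, 35, 40 or 55) and above 2 x baseline otherwise, as now.

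**Secondary suggestion, for the sponsor's hepatology advisers to confirm against the DILI Guidance.** For baselines below 1.5 x ULN, add a stop on a confirmed ALT or AST value above 4.5 x ULN. This is what the existing rule gives at its lower boundary, so it removes the step there.

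**Cost.** Amendment wording and a few unscheduled blood tests; ALT and AST are already collected. The added stop could also cost data. The first on-treatment sample is at Week 6, while 4.4 asks for a biopsy only after at least 12 weeks of treatment, and SAP 6.8 does not carry baseline forward. A patient stopped before 12 weeks may therefore give no primary-endpoint value. In arms of 6, 6 and 3, one such patient is 1/6 = 17% of an active arm or 1/3 = 33% of placebo. An early stop chosen at the observe-or-stop step would carry the same loss.
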